6.5 Blastocyst Transfer

Transfer is performed on day 5 (blastocyst stage) after oocyte retrieval.

The subject-related procedures are described below.

- Transfer of a single blastocyst of the best quality available
[*note*: only applicable for subjects who underwent triggering of final follicular maturation with hCG. Subjects who were administered GnRH agonist will not undergo transfer in this cycle]
- Dispensing of progesterone for luteal phase support. Progesterone support should be continued until the day of the clinical pregnancy visit, but can be terminated earlier in case of menses, a negative β hCG test or pregnancy loss.
- Drug accountability of progesterone
- Recording of use of any concomitant medication
- Recording of adverse events

For subjects with blastocyst transfer, the next visit is the β hCG test visit which must be scheduled 13-15 days after transfer (section 6.6). Subject with no blastocyst transfer will proceed to end-of-trial assessments.

6.6 β hCG Test

Subjects who have undergone transfer must attend a visit 13-15 days after transfer, unless the subject experiences a full menstrual bleeding following transfer, then the β hCG test must be performed 7-15 days after transfer. The β hCG test is mandatory for all subjects who have undergone transfer, irrespective of bleeding.

The following must take place:

- Blood collection for central laboratory analysis of β hCG
- Dispensing of progesterone for luteal phase support, if applicable
- Drug accountability of progesterone
- Recording of use of any concomitant medication
- Recording of adverse events

The blood sample will be analysed for β hCG by a central laboratory and evaluated according to the central laboratory's reference ranges. In case of a doubtful β hCG result, the test may be repeated.

Subjects with a positive β hCG test must attend a clinical pregnancy visit 5-6 weeks after transfer (section 6.7). Subjects with a negative β hCG test must proceed to the end-of-trial assessments (section 6.8).

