6 TRIAL PROCEDURES

The flow of the trial procedures for subjects is shown in Table 6-1.

Table 6-1 Trial Flow Chart – Subject Procedures

| | Screening | Stimulation | | | | Oocyte retrieval | Transfer | Pregnancy monitoring | | End |
|---|-------------------------------|--------------------|-----------------|-----------------------------|--------------------|--------------------------|-----------------|---------------------------|-----------------------------|-----|
| | | During stimulation | | | End-of-stimulation | | | OR | Transfer / cryopreservation | |
| Timing | <60 days before randomisation | Day 1 | Day 6 | Day ≥7 to <20 ^{a)} | End | 36h ±2h after triggering | 5 days after OR | 13-15 days after transfer | 5-6 weeks after transfer | b) |
| Written informed consent | X | | | | | | | | | |
| Inclusion / exclusion criteria | X | X ^{c)} | | | | | | | | |
| Demographics | X | | | | | | | | | |
| Medical history | X | | | | | | | | | |
| Infertility history | X | | | | | | | | | |
| Menstrual history | X | | | | | | | | | |
| Reproductive history | X | | | | | | | | | |
| Body measurements | X | X ^{c)} | | | | | | | | X |
| Physical examination | X | | | | | | | | | X |
| Gynaecological examination | X | | | | | | | | | X |
| Urinary pregnancy test | X | X ^{c)} | | | | | | | | |
| Blood collection, clin chem / haem | X | | | | X | | | | | X |
| Blood collection, endocrine | X ^{e)} | X ^{d) e)} | X ^{f)} | | X ^{f)} | | | | | |
| Ultrasound (ovaries and/or uterus) | | X ^{c)} | X | X | X | | | | X | |
| Vital signs | | X ^{d)} | | | | | | | | X |
| Randomisation | | X | | | | | | | | |
| FE 999049 or FOLLISTIM dispensing | | X ^{g)} | X ^{g)} | X ^{g)} | | | | | | |
| Local tolerability (diary) | | X | X | X | X | X | | | | |
| Concomitant fertility medication dispensing | | | X | X | X | X | X | X | | |
| Oocyte retrieval | | | | | | X | | | | |
| Transfer / cryopreservation | | | | | | | X | | | |
| βhCG test | | | | | | | | X ^{h)} | | |
| Drug accountability | | | X | X | X | X | X | X | X | X |
| Concomitant medication | X | X | X | X | X | X | X | X | X | X |
| Adverse events | X | X | X | X | X | X | X | X | X | X |
| End-of-trial form | | | | | | | | | | X |

a) Visits must be scheduled at least every second day; when 3 follicles of ≥15 mm are observed visits must be scheduled daily.

b) End-of-trial assessments must be performed at the subject's last scheduled visit.

c) Performed before randomisation.

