d) Performed before the first FE 999049 or FOLLISTIM dose.

e) Including AMH analysis

f) Must be drawn at least 8h after the previous administration of FE 999049 or FOLLISTIM and GnRH antagonist, as applicable.

g) If dispensing of FE 999049 or FOLLISTIM in special cases is not possible during stimulation, as an exception all FE 999049 or FOLLISTIM can be dispensed on stimulation day 1.

h) Subjects experiencing a full menstrual bleeding following transfer must have the βhCG test performed 7-15 days after transfer.

AMH: anti-Müllerian hormone; OR: oocyte retrieval.

If trial procedures and/or assessments are to be performed on Sundays, public holidays or outside the opening hours of the clinic, the procedures and/or assessments can be postponed to the upcoming weekday (maximum one day after original visit schedule) or cancelled, if appropriate.

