6.3 Oocyte Retrieval

Oocyte retrieval must take place 36h (± 2 h) after administration of the triggering drug. All oocytes from follicles with an estimated diameter ≥ 12 mm should be retrieved. Below are listed the procedures related to the subjects attending the oocyte retrieval visit, while procedures related to the oocytes are described in section 6.4.

The following must take place at the oocyte retrieval visit:

- Oocyte retrieval
- Dispensing of progesterone for luteal support – must be started on the day after oocyte retrieval [*note*: only applicable for subjects who underwent triggering of final follicular maturation with hCG and who had oocytes retrieved]
- Drug accountability of hCG
- Collection of diary pages
- Recording of use of any concomitant medication
- Recording of adverse events

For subjects with oocytes retrieved following hCG administration, the next visit is the transfer visit 5 days after oocyte retrieval. For subjects with oocytes retrieved following GnRH agonist administration, the oocytes will undergo the procedures described in section 6.4 and blastocysts will be cryopreserved as according to local practice and declaration by JSOG.

Subjects with no oocytes retrieved will proceed to end-of-trial assessments.

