7.3.8 Early OHSS (including Moderate/Severe) and/or Preventive Interventions for Early OHSS

Early OHSS is defined as OHSS with onset ≤ 9 days after triggering of final follicular maturation. Classification of grade is according to Golan's classification system (see section 8.3.1 for details) and all OHSS cases will be graded as mild, moderate or severe. Preventive interventions for early OHSS cover cycle cancellation due to excessive ovarian response, triggering of final follicular maturation with GnRH agonist and administration of dopamine agonist (the latter is only considered as preventive intervention in subjects with ≥ 20 follicles of ≥ 12 mm).

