7.3.9 Late OHSS (including Moderate/Severe)

Late OHSS is defined as OHSS with onset >9 days after triggering of final follicular maturation. Classification of grade is according to Golan's classification system (see section 8.3.1 for details) and all OHSS cases will be graded as mild, moderate or severe.

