3.1 General Design Considerations

This is a randomised, assessor-blind, controlled, parallel groups, multicentre trial assessing the efficacy and safety of FE 999049 in its individualised dosing regimen when used in first cycle Japanese patients aged 20-40 years undergoing controlled ovarian stimulation for IVF/ICSI following a GnRH antagonist protocol.

The trial has been designed to demonstrate non-inferiority of FE 999049 versus an rFSH product approved in Japan, i.e. FOLLISTIM, with respect to number of oocytes retrieved.

Eligible subjects will be randomised in a 1:1 ratio to controlled ovarian stimulation with FE 999049 or FOLLISTIM. Randomisation will be stratified by centre and according to AMH levels at screening (<15 pmol/L and ≥ 15 pmol/L). The randomisation strata by AMH reflect the FE 999049 dosing regimen, and therefore each subject's AMH value is rounded off to the nearest integer before allocation into one of the two strata, <15 pmol/L or ≥ 15 pmol/L. The rounding off rules used for AMH with respect to randomisation strata are identical to those described in Section 5.1.1 "FE 999049 Dosing Regimen" of the protocol. Consequently, the randomisation stratum AMH <15 pmol/L corresponds to the description of the AMH <15 pmol/L category in the FE 999049 dosing regimen, meaning that it includes AMH values up to and including 14.49 pmol/L. The

randomisation stratum AMH ≥ 15 pmol/L includes AMH values from 14.50 pmol/L and higher. These rounding off rules are implemented in the eCRF and used in the automated allocation of subjects into either the AMH < 15 pmol/L or ≥ 15 pmol/L strata.

The last scheduled visit in the main part of the trial is the clinical pregnancy visit (end-of-trial). Non-pregnant subjects should complete the end-of-trial assessments at time of discontinuation. Subjects with a vital pregnancy will be followed for pregnancy outcome as well as neonatal health at birth and at 4 weeks after birth.

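### Triggered women without transfer can leave the trial at about day 6.3–6.9 after triggering, before the 9-day early-OHSS window closes

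*Protocol*

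**What the plan says.** **Endpoint windows.** Protocol 7.3.8 classes OHSS as early if onset is no later than 9 "days after triggering of final follicular maturation". Section 7.3.9 takes the rest: "Late OHSS is defined as OHSS with onset >9 days after triggering of final follicular maturation".

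**Exit without transfer.**
- Protocol 6.5: "Subject with no blastocyst transfer will proceed to end-of-trial assessments".
- Protocol 6.3: "Subjects with no oocytes retrieved will proceed to end-of-trial assessments".
- Protocol Table 6-1, footnote b: "End-of-trial assessments must be performed at the subject's last scheduled visit".
- SAP 3.1: "Non-pregnant subjects should complete the end-of-trial assessments at time of discontinuation".

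For agonist-triggered women, Protocol 6.3 says "For subjects with oocytes retrieved following GnRH agonist administration, the oocytes will undergo the procedures described in section 6.4" and that blastocysts are frozen, but it names no next visit for the woman herself. Section 6.5 rules out transfer for her in this cycle.

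**End of recording.** Protocol 7.3.16 stops adverse-event recording at the end-of-trial visit, and the treatment-emergent definition in SAP 10.2 closes there too. Protocol 8.5 has the investigator report an event that begins later only if it is serious, judged possibly related, and happens to become known. The note under Table 6-1 lets a visit slip by one day at most.

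**The concern.** The endpoint needs at least 9 days of observation after triggering, yet the visit schedule releases some triggered women sooner. Whether a woman is released depends on whether she has a transfer, and that can follow from ovarian response. Protocol 7.3.4 lists ovarian hyperfunction and high progesterone among the adverse events that can cancel a transfer. Neither is itself an OHSS event, so women at risk who were triggered with hCG can leave with no OHSS recorded.

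The secondary objective concerns OHSS frequency together with preventive measures against early OHSS. SAP 10.3 also plans separate analyses of early OHSS, early moderate/severe OHSS and late OHSS. Protocol 8.3.1 promises to evaluate the OHSS rate by type of trigger. Agonist-triggered women never have a transfer, so that evaluation would set women who can all leave early against women who are mostly followed much longer.

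If the comparator has more excessive responders, the loss would fall more heavily on it and shrink any FE 999049 advantage. The documents do not settle whether that happens.

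**Working it through.** The plan states no end-of-trial day for these women, so there is no figure to reproduce. The day follows from the visit windows.

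| Interval | Value | Source |
|---|---|---|
| Trigger to retrieval | 36 ± 2 h = 34–38 h | Protocol 6.3, Table 6-1 |
| Retrieval to insemination | 0–4 h | Protocol 6.4 |
| Insemination to day-5 procedures | 120 ± 3 h = 117–123 h | Protocol 6.4 |
| Transfer to βhCG test | 13–15 d; from 7 d after full menstrual bleeding | Protocol 6.6 |
| Permitted postponement | at most 1 d | Note under Table 6-1 |
| Early-OHSS window | 9 d after trigger | Protocol 7.3.8 |

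**Day of last scheduled visit, oocytes retrieved but no transfer**
- Minimum: 34 + 0 + 117 = 151 h; 151/24 = 6.29 d.
- Maximum: 38 + 4 + 123 = 165 h; 165/24 = 6.88 d.
- With one day's postponement: 7.29–7.88 d, still under 9.

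**Unobserved part of the early window**
- 9 − 6.88 = 2.13 d (23.6%) to 9 − 6.29 = 2.71 d (30.1%).
- With postponement: 1.13–1.71 d (12.5–19.0%).
- No oocytes retrieved, exit at the retrieval visit: 34–38 h = 1.42–1.58 d, leaving 7.42–7.58 d (82–84%).

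**Women with transfer, for comparison**
- Earliest exit, after menstrual bleeding: 6.29 + 7 = 13.3 d to 6.88 + 7 = 13.9 d.
- Ordinary βhCG visit: 6.29 + 13 = 19.3 d to 6.88 + 15 = 21.9 d.

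**Which analyses are exposed.** Under Protocol 7.3.7, agonist triggering and cancellation for excessive response already count as events in the composites with preventive interventions. Untriggered cycles have no 9-day clock. The composites are therefore exposed only through hCG-triggered women with no transfer and no recorded OHSS. Early OHSS alone, early moderate/severe OHSS alone and late OHSS have no such protection.

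**Illustration for early OHSS alone (assumptions, not document figures).** Suppose 10–25% of an arm is triggered without transfer, the OHSS risk is 5–28.3% (the range Protocol 1.1 reports for Japanese patients), and onsets are uniform over days 0–9. Loss per arm = no-transfer share × risk × unobserved fraction.
- Low: 0.10 × 0.05 × 0.236 = 0.12 percentage points, or 0.2 of 164 women.
- High: 0.25 × 0.283 × 0.301 = 2.13 points, or 3.5 of 164.

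Bias in the comparison is the difference between the two arms' losses. It is zero if shares and risks are equal. With no-transfer shares of 25% versus 10% and equal risk:
- Low: 0.15 × 0.05 × 0.236 = 0.18 points.
- High: 0.15 × 0.283 × 0.301 = 1.28 points.

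**The case against.** The strongest case on the other side has five parts.

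1. **Early exit is allowed, not required.** Sections 6.3 and 6.5 give no timing for the step to end-of-trial assessments, and 24–30% is the earliest-exit case. This stands as a limit on the size. The missing timing is itself the gap, and the permitted postponement still ends before day 9.
2. **Day 9 only separates early from late OHSS.** Nothing promises observation to that day, so the passages do not strictly contradict each other. That is fair: this is a design choice. Even so, an incidence defined over a window needs that window to be observed to a similar extent in everyone compared.
3. **OHSS already present is not lost.** Section 8.2.2 dates onset from the first sign and records the worst intensity. Section 8.5 requires follow-up of serious or related events after the last visit, and a transfer cancelled for OHSS already has that event on record. This stands, and confines the loss to onsets after exit.
4. **The illustration is soft.** No document gives the no-transfer shares, their imbalance or the onset distribution. The 5–28.3% range is not specific to early OHSS or to women without transfer, and one of its sources is, by title, a study of ovulation induction in polycystic ovary syndrome. The calculation leaves out women with no oocytes, so 2.1 points is not a bound. For agonist-triggered women the upper end is too high, because Protocol 3.5.4 expects a reduced risk of early moderate/severe OHSS after that trigger. The late-OHSS loss cannot be sized at all.
5. **These are secondary analyses.** They carry no multiplicity control, and the composite named in the objective is mostly protected. This limits the severity, but the separate OHSS analyses are still planned and would be reported.

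None of these points supplies a provision that collects new non-serious OHSS after exit.

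**Conclusion.** The concern holds. As written, the plan lets a triggered woman without transfer finish at day 6.3–6.9 after triggering (at most day 7.9 with the permitted postponement), or at about day 1.5 if no oocytes are retrieved. Non-serious early OHSS beginning after that, and nearly all late OHSS in these women, can go unrecorded. That conclusion rests only on the protocol's windows.

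The effect on the treatment comparison is not known in size or direction. The 0.1–2.1 points per arm and 0–1.3 points between arms depend wholly on the assumptions given with them. The non-inferiority conclusion on oocytes is unaffected. The change should be made because it is cheap and the planned OHSS-only analyses depend on it; confidence is medium.

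**What to change.** **Protocol.** Reconcile 6.3, 6.5, 6.8, Table 6-1 footnote b and 7.3.16 with 7.3.8 and 7.3.9, so that adverse-event and OHSS recording runs past day 9 after triggering for every triggered woman. Either time the end-of-trial visit after the window closes or add one brief adverse-event contact then. Name the next visit for agonist-triggered women in 6.3.

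**SAP.**
- Bring 3.1 and the treatment-emergent definition in 10.2 into line with the extended recording.
- In 10.3, add a table by arm of triggered women not observed through day 9, split by trigger (hCG or agonist) and reason for no transfer.
- State that late OHSS is largely unobserved without transfer.
- Keep the safety analysis set as the main analysis. An analysis restricted to women observed beyond day 9 conditions on a post-randomisation outcome and should be supplementary only.

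**Cost.** Wording changes in both documents, a later final visit or one short contact for triggered women without transfer, and one extra table. This concerns data collection only; no treatment rule changes. If the visits are already complete when this is acted on, the SAP table and the statement on late OHSS can still be added.

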6.7 Clinical Pregnancy

Subjects with a positive β hCG test must attend a visit 5-6 weeks after transfer.

The following must take place:

- Transvaginal ultrasound of uterus to assess any clinical pregnancy
- Drug accountability of progesterone, if applicable
- Recording of use of any concomitant medication
- Recording of adverse events

If at least one gestational sac (either intrauterine or ectopic) is observed, this confirms a clinical pregnancy. If at least one intrauterine gestational sac with fetal heart beat is observed, this confirms a vital pregnancy.

6.8 End-of-Trial

Subjects who have a positive β hCG test and continue to the clinical pregnancy visit will have end-of-trial assessments done at that visit. Subjects who have a negative β hCG test will proceed directly to end-of-trial assessments. Subjects experiencing a full menstrual bleeding following transfer can also proceed to the end-of-trial visit and have the β hCG test performed as part of the end-of-trial assessments, if this occurs 7-15 days after transfer.

The following must take place at the end-of-trial visit:

- Body measurements (body weight)
- Physical examination
- Gynaecological examination
- Vital signs
- Blood collection for central laboratory analysis of clinical chemistry and haematology parameters
- Drug accountability, if applicable
- Recording of use of any concomitant medication
- Recording of adverse events
- Completion of end-of-trial form

These assessments serve to document the subject's physical health at the end of the trial.

6.9 Pregnancy Follow-up

Pregnancy progress and outcome data will be gathered for subjects with a vital pregnancy. Data will be collected on ongoing pregnancy (10-11 weeks after transfer) and pregnancy outcome as well as neonatal health at birth and at 4 weeks after birth. The pregnancy follow-up does not include any interventions but only data collection. The pregnancy follow-up data will be based on reports obtained from the subject's gynaecologist / obstetrician and the subject's Maternal and Child Health Handbook. The data will be retrieved by the trial site, either via the subject's gynaecologist / obstetrician, the subject herself, or other sources, as applicable.

7 TRIAL ASSESSMENTS

7.1 Assessments Related to Primary Endpoint

7.1.1 Number of Oocytes Retrieved

The number of oocytes retrieved will be recorded at the oocyte retrieval visit.

7.2 Assessments Related to Important Secondary Endpoint

7.2.1 Clinical Pregnancy

The clinical pregnancy rate is considered an important secondary endpoint. A transvaginal ultrasound of the uterus will be performed 5-6 weeks after transfer. Clinical pregnancy will be defined as at least one gestational sac, either intrauterine or ectopic. The inclusion of ectopic pregnancies and the lack of specification of heart beat in the definition of clinical pregnancy is in line with the current International Committee Monitoring Assisted Reproductive Technologies (ICMART) and World Health Organization (WHO) glossary on ART terminology.^{b,27}

For intrauterine and ectopic pregnancies, the number of gestational sacs with fetal heart beat as well as without fetal heart beat will be recorded.

7.3 Assessments Related to Secondary Endpoints

7.3.1 β hCG Test

A blood β hCG test must be obtained 13-15 days after transfer, unless the subject experiences a full menstrual bleeding following transfer, then the β hCG test must be performed 7-15 days after transfer. If the test is positive according to the central laboratory's reference ranges, this confirms a positive β hCG. The β hCG test is mandatory for all subjects who have undergone transfer, irrespective of bleeding.

7.3.2 Vital Pregnancy

A transvaginal ultrasound of the uterus will be performed 5-6 weeks after transfer. Vital pregnancy will be defined as at least one intrauterine gestational sac with fetal heart beat 5-6 weeks after transfer.

^b ICMART and WHO glossary on ART terminology: Clinical pregnancy – a pregnancy diagnosed by ultrasonographic visualization of one or more gestational sacs or definitive clinical signs of pregnancy. It includes ectopic pregnancy.

7.3.3 Implantation

Implantation is determined based on the transvaginal ultrasound performed at the clinical pregnancy visit. Implantation rate will be defined as the number of gestational sacs 5-6 weeks after transfer divided by number of blastocysts transferred.

7.3.4 Cycle Cancellation due to Poor or Excessive Ovarian Response or Blastocyst Transfer Cancellation due to Excessive Ovarian Response / OHSS Risk

The reason for each cycle cancellation will be recorded. Cycle cancellations related to inappropriate ovarian response will include poor and excessive follicular development. Cycle cancellation due to poor follicular development is implemented when the investigator judges that ≥ 3 follicles with a diameter ≥ 17 mm cannot be reached by stimulation day 20. Cycle cancellation due to excessive follicular development is implemented when ≥ 25 follicles with a diameter ≥ 12 mm are observed (in case of 25-35 follicles with a diameter ≥ 12 mm, GnRH agonist may be administered). The reason for each blastocyst transfer cancellation will be recorded. Transfer cancellation due to adverse events such as the Medical Dictionary for Regulatory Activities preferred terms (MedDRA PTs) "ovarian hyperfunction", "ovarian hyperstimulation syndrome" and "high progesterone" in subjects with blastocysts available for transfer will be considered as transfer cancellations due to excessive response / OHSS risk.

